2.5.2 Cholesterol Synthesis in the Fetus

Cholesterol is an essential component of fetal development because it is an integral part of the cell membrane and is also the precursor of other steroid hormones such as progesterone.⁷⁷ The majority of fetal cholesterol originates from de novo synthesis (fetus or placenta) rather than from maternal sources. Defects in cholesterol synthesis pathways in the fetus lead to congenital malformations. Six are extremely rare and often lethal. A seventh ($\Delta 7$ reductase) is more common and leads to Smith-Lemli-Optiz syndrome. Fetuses with null mutations in $\Delta 7$ reductase (i.e., they do not synthesize cholesterol) have only

very low amounts of cholesterol in their tissues and blood, confirming the minor role of maternal exogenous sources.⁷⁷ In the presence of normal fetal sterol synthesis, maternal cholesterol supply is of minimal importance.⁷⁷ Additionally, women with abetalipoproteinemia or hypobetalipoproteinemia and those consuming low-cholesterol diets have low plasma cholesterol concentrations during gestation and yet there are no adverse effects on pregnancy or the fetus.⁷⁷

In a group of women with diets different in cholesterol content (from cholesterol-free to high cholesterol) during pregnancy, maternal serum total cholesterol at term ranged from 188 to 291 mg/dL. Switching to a cholesterol-free diet decreased total serum cholesterol from 234 to 187 mg/dL, a 20% drop without any adverse fetal or pregnancy effects.⁷⁸ Similarly, the Tarahumara Indians of Mexico are known to consume little cholesterol/fat and have a low plasma lipid profile. The average total cholesterol and LDL cholesterol are 141 and 89 mg/dL in non-pregnant females and 193 and 122 mg/dL during pregnancy. Although the degree of increase in cholesterol during pregnancy is similar to that observed in women consuming normal diets in other populations, cholesterol levels during pregnancy are still lower in the Tarahumara Indians compared with American women (193 vs. 250–300 mg/dL during pregnancy). Yet no increased rates of congenital malformations or pregnancy complications are observed in this Indian group.⁷⁹ The lower cholesterol levels during pregnancy in these populations are in accordance with the reduction in total cholesterol levels observed with a 40 mg dose of pravastatin.^{80,81} Lower doses of pravastatin would be expected to have a smaller reduction in cholesterol levels. In summary, concerns regarding the effect of maternal intake of pravastatin during pregnancy on fetal cholesterol are not supported.

2.5.3 Fetal Brain Development

Pravastatin is unlikely to cross to the fetal brain as it has limited ability to cross the blood-brain barrier. No traces of pravastatin have been found in the cerebrospinal fluid of adult patients taking pravastatin. Pravastatin is a substrate of P-glycoprotein, an efflux pump in the endothelial cells of the blood-brain barrier.⁷² This supports the previously reported cohort studies that did not find any association between pravastatin exposure during early pregnancy and risk of congenital (especially central nervous system) malformations.

2.5.3.1 Preclinical Studies

In pregnant rats given oral gavage doses of 10, 100, and 1000 mg/kg/day from gestation day 17 through lactation day 21 (weaning), increased mortality of offspring and developmental delays were observed at 100 mg/kg/day systemic exposure, twelve times the human exposure at 80 mg/day (maximum recommended human dose, MRHD) based on body surface area (mg/m²).⁸²

The approval package for Pravachol⁸³ reports that when administered to juvenile rats on postnatal days 4 through 80 at 5–45 mg/kg/day, no drug related changes were observed at 5 mg/kg/day. At 15 and 45 mg/kg/day, slight thinning of the corpus callosum at the end of the recovery period was observed. This finding was not evident in rats at the completion of the dosing period, and was not associated with any inflammatory or degenerative changes in the brain. The biologic relevance of the corpus callosum finding was noted to be uncertain. Neurobehavioral changes (enhanced acoustic startle responses and increased errors in water-maze learning) combined with evidence of generalized toxicity were noted at 45 mg/kg/day during the later part of the recovery period.

It was also reported that studies performed since the marketing approval in 1991 consisted of direct dosing neonatal rats at postnatal days 4 to 80 to address neurodevelopmental events specifically (such as myelination) which occur prenatally in humans but postnatally in the rat. Decreased thickness of the corpus callosum was observed at 20X systemic exposure following an 80 mg clinical dose. At higher exposures (40X) this finding in conjunction with decreased relative brain weights and functional alterations in reflex response (acoustical startle) and learning (water-maze) were observed.

Together these studies were deemed to indicate a perturbation in myelination. The No Observed Adverse Effect Level (NOAEL) of 5 mg/kg/day or 5X systemic exposure following an 80 mg human dose was established in the rat neonatal neurodevelopmental study.”

Data from a preeclampsia-like rodent model in which dams were treated with pravastatin at a dose of 5 mg/kg/day, demonstrated that 6-month old mice offspring born to preeclamptic dams, and who were exposed in-utero to pravastatin from embryo day 9 till birth performed similarly on assays testing vestibular function, balance, and coordination (righting reflex, negative geotaxis, balance beam, and climbing) compared with control offspring born to non-preeclamptic dams. In fact, pravastatin corrected some of the findings observed in offspring from preeclamptic dams in the placebo group.⁸⁴ Additionally, whole brains from these offspring underwent magnetic resonance imaging (MRI) to evaluate the volumes of 28 regions of interest, including areas involved in adaptation and motor, spatial and sensory function. Offspring born to preeclamptic dams and who were exposed to pravastatin in utero had similar brain volumes compared with those born to non-preeclamptic dams. Similar to the functional data, pravastatin prevented the changes seen in mice offspring born to preeclamptic dams in the placebo group (changes seen in the fimbria, periaqueductal gray, stria medullaris, ventricles, lateral globus pallidus, neocortex, fasciculus retroflexus, inferior colliculus, thalamus, and lateral globus pallidus).⁸⁵ Neuronal quantification exhibited decreased cell counts in the neocortex of offspring born to preeclamptic dams, and prenatal pravastatin treatment prevented these changes.

Data from another murine model of preeclampsia (C1q KO model) in which mice destined to develop preeclampsia were treated with pravastatin 10 microgram i.p., a human equivalent dose of 20 mg, showed that pravastatin treatment in pregnancy prevented the microglial activation seen in the brains of 30 day old (P30) offspring born to preeclamptic dams assigned to placebo.⁸⁶

Other studies using other statins showed that simvastatin attenuates the hypomyelination induced by hypoxia-ischemia injury in PND 7 rats, through its anti-inflammatory properties via suppression of microglial activation.⁸⁷ Simvastatin also improves functional outcomes in neonatal rat stroke models through reduced cytokine induction and dampening of the inflammatory response.⁸⁸

2.5.3.2 Clinical Studies

Data from the NICHD Obstetrics Fetal Pharmacology Research Centers (OPRC) Network pilot studies in which pravastatin 10 mg and 20 mg were used (described in section 2.6.2), showed the following: 1) the only central nervous system anomaly observed was ventriculomegaly and was seen in a patient who received placebo, 2) there were no cases of holoprosencephaly or agenesis (or hypogenesis) of the corpus callosum on prenatal ultrasound examination, 3) neurologic injury markers in the cord blood (NSE and S100-B) were not different between the pravastatin or placebo arms of either cohort, 4) all newborns in both cohorts who were exposed to pravastatin passed either the Auditory Brain Stem Response (ABR) or Otoacoustic Emissions (OAE) tests before discharge from the hospital after birth, 5) neither the 10 mg dose nor the 20 mg dose of pravastatin resulted in a difference in neonatal head circumference compared with placebo (34 ± 1.8 cm vs. 34.2 ± 0.6 cm, $p=0.6$ and 31.1 ± 4.7 vs. 32.4 ± 3.1 , $p=0.5$), and 6) pravastatin drug concentrations in the cord blood were undetectable for the majority of newborns born to mothers on active treatment for both the 10 mg cohort (5 out of 7 available cord blood concentrations were less than the lower limits of quantification (LLOQ) and the 20 mg cohort (6 out of 7 available cord blood concentrations were less than LLOQ).

2.5.4 Maternal Safety

A thorough evaluation of the safety profile for a therapeutic intervention for preeclampsia prevention must also focus on potential maternal risks. Pooled data from the large-scale placebo-controlled randomized clinical trials in non-pregnant patients have provided significant information on the risks and side effects associated with use of pravastatin and have reassured clinicians that serious side effects (e.g.,

liver injury and rhabdomyolysis) are extremely rare. In general, pravastatin is considered to be safe and tolerable. Three long-term (4.8- to 5.9-year) placebo-controlled trials of pravastatin (the West of Scotland Coronary Prevention Study, the Cholesterol and Recurrent Events Study, and the Long-term Intervention with Pravastatin in Ischemic Disease Study) collectively included 19,592 patients randomized to pravastatin (40 mg daily) or placebo and accumulated more than 112,000 person-years of exposure.^{80,81,89} During five years of exposure, the rates of marked elevations of aminotransferases were low and similar between the two groups (<1.2%). In addition, experience with pravastatin in these trials suggests that liver function test abnormalities observed during pravastatin therapy were usually asymptomatic, not associated with cholestasis, and did not appear to be related to treatment duration. On the other hand, the rate of myopathy, defined as muscle aching or muscle weakness with elevated creatine phosphokinase (CPK) serum levels greater than 10 times the upper limit of normal, was rare (<0.1%) in pravastatin clinical trials.^{61,90}

Adverse events were assessed in an indirect comparison meta-analysis of all statins including pravastatin (higher doses than proposed in this trial). In pravastatin exposed patients, rhabdomyolysis occurred in 120 (0.6%; data available from 10 randomized trials; 40,394 individuals), increased AST (3xULN) occurred in 244 (1.4%; data available from seven randomized trials; 35,350 individuals), increased ALT (3xULN) occurred in 134 (1.8%; data available from four randomized trials; 15,200 individuals), and 10 fold increase in creatine kinase (CK) without muscle symptoms occurred in 156 (1.2%; data available from seven randomized trials; 26,407 individuals).⁹¹

Regarding side effects, pravastatin is generally considered safe, and side effects associated with its use are usually mild and transient. In short-term (4-month) placebo-controlled trials, the rate of study drug discontinuation was similar between pravastatin- and placebo-treated patients (1.7% vs. 1.2%).⁶¹ Of patients on pravastatin (any dose) or placebo, 10.1% and 10.2% reported localized muscle pain; however, only 1.4% and 1.5% of these events were attributed to study medication. The rate of myalgia, regardless of causality, was 2.3%; however, that attributed to pravastatin use was 0.6%.⁶¹ On the other hand, data from 21,483 patients from seven long-term (1.9- to 5.1-year) placebo-controlled pravastatin (40 mg) trials showed similar safety and tolerability profiles for pravastatin compared with placebo (47,613 patient-years of exposure to pravastatin). In these long-term trials, the most common reasons for discontinuation were mild, nonspecific gastrointestinal side effects.⁶¹ Finally in the PRIMO observational study, the rate of muscle related symptoms with pravastatin 40 mg was 10.9%.⁹² Findings from the OPRC pilot trials are similar to data from non-pregnant subjects and are summarized in section 2.6.2.

2.5.5 Interactions with Other Medications

Studies regarding the interaction of pravastatin and other medications did not include pregnant women. The effects of pregnancy on such interactions are unknown.

The concurrent use of erythromycin, niacin, cyclosporine, or fibrates with HMG-CoA reductase inhibitors other than pravastatin has been thought to be associated with increased risk of myopathy. However, except for fibrates, the risk has not been proven with concurrent use of these medications and pravastatin. Therefore, it is recommended not to co-administer pravastatin with fibrates and colchicines; and to reduce the pravastatin dose when given together with niacin.⁶¹

On the other hand, inhibitors of cytochrome P450 3A4- such as diltiazem, itraconazole, ketoconazole, mibefradil, and erythromycin- were not found to significantly affect the pharmacokinetic properties of pravastatin when used concurrently. That may be explained by the fact that pravastatin is a weak substrate of cytochrome P450 3A4.⁷²

The concurrent use of bile acid resins (cholestyramine, colestipol) and pravastatin resulted in approximately 40-50% decrease in the mean area under the curve (AUC) of pravastatin. Therefore, it is recommended to administer pravastatin at least 1 hour before or 4 hours after the administration of the resin. For pravastatin and cimetidine (H2-receptor antagonist), there was 30% increase in the AUC of

pravastatin compared with when pravastatin was taken alone. On the other hand, when it was taken concomitantly with digoxin, there were no differences in digoxin bioavailability, but the AUC of pravastatin increased by 23%. Concomitant use with clarithromycin resulted in increase in pravastatin AUC by 110%, therefore it is recommended to limit pravastatin to 40 mg daily when used concomitantly with clarithromycin. Regarding cyclosporin, studies in transplant patients taking both medications concurrently did not show any significant effect on cyclosporine levels, however, pravastatin AUC was increased by 282% and Cmax by 327%; and it is recommended to limit pravastatin dosage to 20 mg once daily for concomitant use with cyclosporine.^{61,72}

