3.4.3 Exclusion Criteria

1. Monoamniotic gestation because of the risk of fetal demise
2. Known chromosomal, genetic or major malformations
3. Fetal demise or planned termination of pregnancy. Selective reduction by 13 weeks 6 days gestation, from triplets to twins or twins to singleton is not an exclusion.
4. Contraindications for statin therapy:
 - a. Hypersensitivity to pravastatin or any component of the product
 - b. Active liver disease: acute hepatitis or chronic active hepatitis
5. Statin use in current pregnancy
6. Patients with any of the following medical conditions:
 - a. Uncontrolled hypothyroidism with a TSH level above 10 mIU/L, because of increased risk of myopathy
 - b. HIV positive, because of increased risk of myopathy with use of protease inhibitors
 - c. Chronic renal disease with baseline serum creatinine ≥ 1.5 mg/dL, because of association with adverse pregnancy outcomes
7. Current use of concomitant medication with potential for drug interaction with statins (i.e., cyclosporine, fibrates, niacin, erythromycin). Patients will not be excluded if the drug is discontinued (at least one week) prior to randomization.
8. Participating in another intervention study that influences the primary outcome in this study
9. Plan to deliver in a non-network site
10. Participation in this trial in a previous pregnancy. Patients who were screened in a previous pregnancy, but not randomized, do not have to be excluded.

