4.5 Patient Management

Use of low dose aspirin is recommended, as it is currently standard of care in the U.S. for women with prior preeclampsia according to the ACOG guidelines.

Patients' pregnancy management (including antenatal testing, ultrasounds, control of hypertension, inpatient vs. outpatient management, and mode and timing of delivery) will be performed as recommended by standard prenatal care as defined by the respective participating institution. Inpatient vs. outpatient management of patients with preeclampsia (without severe features), single vs. double courses of antenatal corticosteroids in the setting of preterm labor, and other obstetric interventions will be left to the discretion of the treating physician.

Although chronic use of the drugs that may have potential significant interactions with pravastatin are listed as an exclusion criteria, the occasion may arise that a pregnant woman in the study may require one or more of these medications. Therefore, and to avoid any potential (or unknown) interactions; patients and providers in this study will be advised of the following:

- Study drug should be taken at least 1 hour before or 4 hours after the administration of cholestyramine.
- Cimetidine (H2-receptor antagonists) should be taken at least 1 hour before study drug.
- There is no need to change the timing or stop study drug if also taking aspirin, digoxin, or diltiazem.
- In the event that a patient requires erythromycin (e.g., rupture of membranes), an alternative antibiotic will be recommended if available. If not, the study drug will be stopped for the duration of erythromycin intake (usually 7 days). The study drug will be resumed at the end of that period.

In this study, the following events that could be related to pravastatin use will be defined and monitored as Adverse Events of Special Interest (AESI).

- Myalgia: diffuse muscle pain, cramps, or soreness without elevation in CK
- Muscle weakness: muscle weakness documented on physical exam without elevation in CK
- Myositis: muscle symptoms (myalgia or weakness) with CK elevations between 3 and 10 times upper limit of normal (ULN) in pregnancy or between 3 and 10 times the baseline CK value, whichever is higher
- Myopathy: muscle symptoms (myalgia or weakness) plus CK $\geq 10x$ ULN or 10x baseline CK

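### Section 2.5.5 advises against giving pravastatin with colchicine, but exclusion criterion 7's closed drug list does not name it

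*Combined protocol and SAP*

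**What the plan says.** Section 2.5.5 (Interactions with Other Medications) first describes a myopathy concern for statins other than pravastatin when taken with erythromycin, niacin, cyclosporine or fibrates. It adds that "except for fibrates, the risk has not been proven with concurrent use of these medications and pravastatin". It then gives its advice for pravastatin: "it is recommended not to co-administer pravastatin with fibrates and colchicines", and, for niacin, "to reduce the pravastatin dose when given together with niacin".

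Section 3.4.3 (Exclusion Criteria), criterion 7, excludes "Current use of concomitant medication with potential for drug interaction with statins (i.e., cyclosporine, fibrates, niacin, erythromycin". The allowance that follows reads "Patients will not be excluded if the drug is discontinued (at least one week) prior to randomization".

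Section 4.5 (Patient Management) introduces its on-study instructions with the premise that "chronic use of the drugs that may have potential significant interactions with pravastatin are listed as an exclusion criteria". It then covers cholestyramine, cimetidine, aspirin, digoxin, diltiazem and erythromycin. Erythromycin is the only one of these for which study drug is stopped, and then only if no alternative antibiotic is available.

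**The concern.** The background section and the operative eligibility rule do not agree on colchicine. Section 2.5.5 names two drugs or classes that should not be given with pravastatin, and criterion 7 names one of them. A site that applies the list as written has no stated ground for excluding a current colchicine user, while a site that reads section 2.5.5 alongside it probably would exclude her. The same woman could therefore be eligible at one center and not at another, and the first center would be starting a combination the protocol advises against. Section 2.5.5 also says that the interaction studies did not include pregnant women and that the effect of pregnancy on these interactions is unknown, which favors caution at entry. What is at stake is participant safety and uniform eligibility, not the validity of the statistical design.

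**Working it through.** No arithmetic applies and the plan has no figure to reproduce. The check compares the relevant texts.

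1. **Drugs section 2.5.5 says not to combine with pravastatin.** There are two: fibrates and colchicine.

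2. **Drugs criterion 7 names.** There are four: cyclosporine, fibrates, niacin and erythromycin. The overlap with step 1 is fibrates only, so one of the two is covered by name.

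3. **Is the list open or closed?** The lead phrase of criterion 7 refers generally to potential interaction with statins, which is wide enough to take in colchicine. The parenthesis begins with 'i.e.', which defines the group, and not 'e.g.', which would illustrate it. As written, the list is closed.

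4. **Where the list appears to come from.** The four names are the same four that section 2.5.5 gives in its sentence on myopathy with statins other than pravastatin, and criterion 7 is likewise worded for statins as a class. The list is therefore a coherent precautionary choice. It still leaves out a drug named in the pravastatin-specific advice of the same paragraph, and no reason is given.

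5. **Does another criterion close the gap?** Criterion 4 (contraindications for statin therapy) covers hypersensitivity and active liver disease only. Criteria 6a and 6b exclude uncontrolled hypothyroidism and HIV on grounds of myopathy risk, which shows that the protocol does screen for such risk at entry, but neither concerns colchicine. No other mention of colchicine was found in the protocol text supplied.

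6. **Does the premise of section 4.5 hold?** It says that the drugs with potentially significant interactions are listed as exclusions. If the drugs that section 2.5.5 says not to co-administer are among these, the premise holds for fibrates and does not clearly hold for colchicine.

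7. **On-study instruction.** Of the four drugs in criterion 7, only erythromycin has an instruction in section 4.5. Fibrates, niacin and cyclosporine have none, and neither does colchicine. This gap is general and not specific to colchicine.

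**The case against.** The strongest reply is that criterion 7 already reaches colchicine through its general phrase, so an investigator who reads it with section 2.5.5 has grounds to exclude. That is a fair reading of intent, but it depends on treating 'i.e.' as 'e.g.', and sites need not all do so.

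A second reply is that other safeguards exist. Medications and creatine kinase are recorded at baseline (section 4.3), medications are listed monthly (section 4.4), there are hold and stop rules for muscle symptoms (section 4.5), and muscle events are monitored continuously (section 5.4.3). These stand and limit the consequence. The records would reveal colchicine use but carry no instruction about it, and the muscle rules act only after symptoms or events.

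A third reply is that the basis for the colchicine advice cannot be examined. Nothing before it in section 2.5.5 mentions colchicine, and it rests on the cited package insert. This stands: the documents give no mechanism, event rate or strength of evidence. They show that two texts disagree, not how large the risk is.

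Three stronger readings are tempting and are not supported:

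- *Colchicine was dropped by a drafting slip when fibrates were copied across.* The exact match with the earlier four-drug sentence points to a different source for the list.
- *The listed drugs are less risky than the omitted one.* For cyclosporine, section 2.5.5 says "it is recommended to limit pravastatin dosage to 20 mg once daily for concomitant use with cyclosporine", which is the trial dose, but it also reports pravastatin AUC up by 282% and Cmax by 327%. For erythromycin, it says only that inhibitors of its class "were not found to significantly affect the pharmacokinetic properties of pravastatin when used concurrently", which is an observation and not advice. Wording alone does not rank these risks.
- *Staff have no instruction if colchicine is started during the study.* Section 4.5 has none, but section 1.3 refers to a manual of operations with detailed procedures, which is not among the documents.

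**Conclusion.** The mismatch holds. Section 2.5.5 advises against the combination, criterion 7 as literally worded does not exclude it, and section 4.5 assumes an exclusion list that is not clearly complete. The size is small: one drug, omitted from one criterion, with use assumed to be very rare because the documents give no rate. No sample size, power, type I error or analysis is affected.

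Confidence is high on the textual disagreement, which rests on reading 'i.e.' as closing the list. A reader might go further and infer that participants face a known hazard. The documents do not show that, and this remains a consistency correction worth making because it is nearly free. The absence of on-study instructions in section 4.5 is a lesser matter. It is shared with fibrates, niacin and cyclosporine, and sites or the manual of operations may already deal with it.

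**What to change.** Add colchicine to the list in criterion 7, under the existing allowance for women who stop the drug before randomization. The one-week interval is the protocol's own for the drugs now listed. No document gives a washout for colchicine, so the sponsor should confirm that one week suits it. The cost is one drug name in an amendment and the loss of a very small number of women who cannot stop colchicine.

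Optionally, extend the erythromycin approach in section 4.5 to the drugs that section 2.5.5 says not to co-administer, namely fibrates and colchicine: use an alternative if there is one; otherwise hold study drug in either arm, with the blind kept, while the other drug is taken. That costs one sentence. A woman on long-term treatment could lose study-drug exposure for the rest of her pregnancy, but she would still be encouraged to continue study visits (section 4.5) and would be analyzed as randomized (section 6.3).
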